CLINICAL TRIAL DOCUMENT COVER PAGE

Official Title of the Study:

Adherence to the Mediterranean Diet Following Nutritional Education and Its Effect on Anxiety, Depression, Fatigue, and Sleep Quality Among a Group of Lactating Women in Jordan: An Interventional Study

NCT Number: Not yet assigned

Document Type: Protocol / Statistical Analysis Plan

Version Number: Version 1.0

Document Date: May 2026

Sponsor / Institution: Applied Science Private University

Principal Investigator: [name]

Contact Information: [contact]

Title of the project

Adherence to the Mediterranean Diet Following Nutritional Education and Its Effect on Anxiety, Depression, Fatigue, and Sleep Quality Among a Group of Lactating Women in Jordan: An Interventional Study.

The outcome:

The aim of our study is to compare the degree of adherence to MedDiet between women who received educational and nutritional interventions during 6 months of follow-up and those without such interventions, and to examine the impact of these interventions on mothers' nutritional status, anthropometrics, and mental health.

The objectives:

The objectives of the current study are:

1. Investigate the impact of an educational intervention on MedDiet among a group of lactating women aged 18-40 years and above in Jordan over a six-month follow-up period.
2. Investigate the relationship between MedDiet adherence, obesity, and mental health. among a group of lactating women aged 18-40 years and above in Jordan over a six-month follow-up period.

Protocol**Study design and setting**

An intervention study is conducted for lactating mothers with follow-up at 3 and 6 months. Participant recruitment focuses on lactating women with infants aged 1-2 months.

The study is conducted at the Ministry of Health's childbirth vaccination clinics in Amman and Irbid, Jordan. The clinics have a fine reputation for maternal and child health services with organized working and research systems.

Ethical considerations

Ethical approval was obtained from the Ministry of Health (MOH/REC/2024/502) and the IRB at Philadelphia University (1/1/2024-2025). The research complies with the ethical principles for medical research involving human subjects of the Helsinki Declaration. (“World Medical Association Declaration of Helsinki: Ethical Principles for Medical Research Involving Human Subjects,” 2014). All participants provide written informed consent before starting, and their right to privacy, anonymity, voluntary participation, and confidentiality are observed.

Participants

Participants consisted of eligible lactating women aged 18–40. The exclusion criteria are (1) all women aged below 18 or above 40, (2) lactating women diagnosed with mental diseases, and (3) women who were already on supplementation for managing deficiencies such as iron, B12, and vitamin D or hormonal disturbances, mainly thyroxine.

Sample size:

The sample size is calculated using 95 % confidence and an RR of 1.9, considering a 20 % non-response rate in cohorts (Rahman et al., 2007), which assumes the number of participants to be 180 based on the population of all eligible candidates who are sequentially enrolled in the study for 6 months, with an expected total research duration of 8 months.

Instruments

Validated Arabic public-domain questionnaires are distributed to collect demographic data, including age, weight, pre-pregnancy BMI, nationality, income, education, employment, insurance status, marital status, gestational age, number of children, and smoking status. Also, anthropometry and possible confounders such as physical and psychological abuse. All participants are interviewed face-to-face, and trained nutrition researchers fill out questionnaires.

A. Questionnaires:

Validated Arabic version of:

- **MEDAS:** A 14-item Mediterranean Diet Adherence Screener (14-MEDAS) is used to assess the adherence of eligible participants to MedDiet
- **Food Frequency questionnaire:** The questionnaire assesses habitual dietary intake by questioning the frequency with which food items are consumed over one week. It is adjusted in a cultural context; foods not typically used in the Jordanian diet are omitted, while foods typically used are added (Tayyem et al., 2014).
- **A diet quality questionnaire,** the food-based diet quality index, was created by synthesizing current nutrition knowledge. The questionnaire includes 14 "healthy" and 7 "unhealthy" food components known to affect health and prevent major diet-related diseases (Kronsteiner-Gicevic et al., 2021).
- **Depression, Anxiety, and Stress Scale-21 Items (DASS-21)** is a set of three self-report scales developed to measure the emotional states of depression, anxiety, and stress that can effectively assess mental health symptoms for individuals (Bryson et al., 2021; Effati-Daryani et al., 2020; Khouj et al., 2022).
- **Modified Fatigue Impact Scale (MFIS):** The MFIS is a modified version of the FIS that measures physical, cognitive, and psychosocial fatigue. Participants rate the impact of fatigue on their lives over the past 4 weeks on a scale of 0 (no problem) to 4 (extreme problem) (Strober et al., 2020).
- **The Pittsburgh Sleep Quality Index (PSQI)** measures general sleep quality and is a recommended questionnaire for studying global sleep and insomnia symptoms (Zitser et al., 2022).
- **The Beck Depression Inventory (BDII):** This depression self-report measure has been extensively researched and used in clinical and non-clinical populations. It has strong psychometric properties and is widely implemented in depression-related research (Arnarson et al., 2008).
- **SF-36 ARABIC**

B. Educational Intervention:

The participants are divided into three groups. The first group receives nutritional education from a qualified nutritionist and a brochure about the Mediterranean diet. The intervention includes the importance and health benefits of MedDiet, mental health, good food sources, and lifestyle practices to maintain good nutritional status and mental health during lactation, with regular reminders about the importance of a healthy diet. These reminders are communicated through channels such as text messages or WhatsApp. The second group receives only the brochure. The brochure includes the definition and components of MedDiet, its health benefits, food sources, food alternatives rich in minerals such as iron, calcium, and B vitamins, and the importance of healthy lifestyles, including increasing physical activity and avoiding smoking. Lastly, the third group is the control group. They do not receive educational interventions or brochures. However, due to ethical considerations, the control group will receive the education and brochure after completing the study.

Statistical analysis

The database will be built in Microsoft Excel, with duplicate entries to verify data consistency. Data processing and analysis will be performed using SPSS 24 (IBM, NY, USA).

Descriptive statistics and correlations for all quantitative and categorical study variables are calculated at baseline and at the end of the study to present the prevalence of depression, anxiety, and stress severity. Appropriate descriptive statistics such as percentages, means, and standard deviation summarize the data depending on the variable type. The Shapiro–Wilk test will be applied to assess data normality. Data are described using means (SD) and percentages. The student's t-test will be used to compare the means and medians of independent variables between groups; Pearson's Chi-Square test will be used for categorical data to test for association and probability, especially the relationship between sociodemographic variables, nutritional status, and the severity of depression, anxiety, and stress. Moreover, the significance level was set at $p < 0.05$, along with logistic regression, to identify the determinants of the severity of depression, anxiety, and stress among pregnant women attending the clinics. For the ordinal regression modeling, the severity is coded as normal = 0, mild = 1, moderate = 2, and severe = 3. The multivariable ordinal logistic regression model includes Variables statistically significant at $P \leq 0.05$ in the bivariate analyses.

References:

- Arnarson, P. Ö., Ólason, D. P., Smári, J., & Sigurdsson, J. F. (2008). The Beck Depression Inventory Second Edition (BDI-II): Psychometric properties in Icelandic student and patient populations. *Nordic Journal of Psychiatry*, 62(5), 360–365. <https://doi.org/10.1080/08039480801962681>

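### Baseline fatigue is recalled over different postpartum periods, and neither the variable list nor any planned comparison names time since delivery

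*Combined protocol and SAP*

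**What the plan says.** **Timing.** Under Study design and setting: "Participant recruitment focuses on lactating women with infants aged 1-2 months". The same section gives the schedule: "An intervention study is conducted for lactating mothers with follow-up at 3 and 6 months". No visit windows are given, and the visits are not tied to infant age. The Participants section sets limits on maternal age, diagnosed mental disease and supplementation or thyroxine use. It sets none on infant age, so the 1-2 month range is a recruitment focus and not an eligibility criterion.

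**Recall.** Under Questionnaires, for the MFIS: "Participants rate the impact of fatigue on their lives over the past 4 weeks". No recall period is given there for the PSQI, DASS-21 or Beck inventory.

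**Recorded variables.** Under Instruments, the questionnaires "collect demographic data, including age, weight, pre-pregnancy BMI, nationality, income, education, employment, insurance status, marital status" and then "gestational age, number of children, and smoking status". The only example of a confounder is in the phrase "possible confounders such as physical and psychological abuse". Infant age, date of delivery and weeks since birth are not named.

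**Groups and analysis.** The Educational Intervention section splits the women into three groups without saying how. The Statistical analysis section compares group means by Student's t-test with no covariate. Its regression models concern the severity of depression, anxiety and stress, with covariates chosen by bivariate significance. No adjusted model is described for fatigue, sleep or weight.

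**The concern.** A woman enrolled when her infant is 1 month old reports on nearly the whole time since delivery. One enrolled at 2 months reports on a period that leaves out the first month. Both scores count as baseline. It is plausible, though the documents do not show it, that fatigue, sleep and weight change in these weeks for reasons unrelated to diet.

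If the three groups differed in infant age at entry, part of any difference between them could reflect time since delivery and not education. Balance cannot be taken for granted, because no randomisation or stratification is stated, and an unadjusted t-test would not correct an imbalance. Even with balanced groups, the spread adds some variance to the scores.

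**Working it through.** There is no stated figure in the plan to reproduce on this point. The check is interval arithmetic followed by a scenario for size.

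**Inputs from the documents:** infant age 1-2 months at recruitment; MFIS recall of 4 weeks (28 days); 180 participants; three groups.

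**Assumptions:** 1 month = 365.25/12 = 30.44 days (4.35 weeks); infant age uniform between 1 and 2 months; equal groups of 180/3 = 60; MFIS slope with time since delivery 0.5-2 points per week; MFIS SD 15. The documents give no MFIS mean, SD or time trend.

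**1. Recall windows at the two ends** (age minus 28 days, to age)
- Infant aged 1 month: days 2.4 to 30.4 after birth.
- Infant aged 2 months: days 32.9 to 60.9.
- Overlap 0 days; gap 32.9 − 30.4 ≈ 2.4 days. With months of 30 days the gap is 2 days; with months of 4 weeks the windows touch.

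**2. Typical pair of women** (window width W = 30.44 days, recall L = 28 days)
- Mean absolute age difference = W/3 = 10.1 days, or 1.45 weeks.
- Mean overlap = L²/W − L³/(3W²) = 25.76 − 7.90 = 17.9 days; 17.9/28 = 64%.
- Probability of no overlap = ((W − L)/W)² = (2.44/30.44)² = 0.0064, about 0.6% of pairs.

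These figures depend on how the age range is read. If it means completed months, up to just under 3, then W = 60.9 days, the gap at the ends is about 33 days, and (32.9/60.9)² = 29% of pairs share none. The documents do not define the term; the narrower reading is used below.

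**3. Imbalance expected by chance**
- SD of uniform age = 4.35/√12 = 1.255 weeks.
- SE of the difference in mean age between two groups = 1.255 × √(2/60) = 0.23 weeks.
- 95% of differences lie within 1.96 × 0.23 ≈ 0.45 weeks.
- Effect on MFIS = slope × difference: 0.5 × 0.45 = 0.2 points to 2 × 0.45 = 0.9 points. Divided by 15, this is 0.015 to 0.06 SD.

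**4. Systematic imbalance**
- If one group came wholly from the younger half of the window and another wholly from the older half, mean ages would differ by 4.35/2 = 2.17 weeks.
- A 1-week difference therefore needs a gap of 1/2.17 = 46 percentage points in the share drawn from each half.
- At differences of 1-2 weeks, the effect would be 0.5 × 1 = 0.5 to 2 × 2 = 4 points, or 0.03 to 0.27 SD.

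**5. Added noise if groups are balanced**
- SD from infant age = slope × 1.255 = 0.6 to 2.5 points.
- Share of a total variance of 15² = 225: 0.2% to 2.8%.

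**The case against.** The strongest reply is that a one-month recruitment window is an ordinary choice and that its consequences are small. Much of this stands.

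- **Non-overlap.** A reader might infer that baseline fatigue scores generally refer to separate periods. They do not: on the narrower reading of the age range, and with uniform ages, typical pairs share about two thirds of the recall.
- **Recording.** A reader might infer that infant age is not collected. The variable list is introduced as inclusive, and infant age must be known to recruit as described. The documents support only that it is not named.
- **Size.** A reader might infer a bias of up to 0.27 SD. That needs almost complete separation of groups by infant age. Nothing in the documents links group assignment to infant age, and sequential enrolment alone does not create a link.
- **Which analysis.** The plan defines no MFIS change score. A slope that stayed constant through follow-up would cancel from change scores. If groups are instead compared at 6 months, with infants about 7-8 months old, an early postpartum slope may no longer apply.
- **Instruments.** The recall argument is shown only for the MFIS. For sleep, mood and weight the point is time since delivery itself, not a recall window.
- **Root cause.** Any bias would come from the unstated allocation method and the lack of an adjusted model, both larger gaps than this one.

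What the reply does not remove is that allocation is not stated to be random, so chance balance is itself an assumption, and that nothing in the plan would show or correct an imbalance in time since delivery. Allocation by clinic or by calendar period, which the plan does not exclude, could produce one.

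**Conclusion.** The concern holds as a minor, cheaply corrected gap. Baseline MFIS scores cover postpartum periods that differ between women, mostly by part of the recall window, and the plan neither names time since delivery nor adjusts for it. Its effect on group comparisons cannot be computed from the documents.

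If infant age is uniform over a one-month window, with 60 per group and allocation unrelated to infant age, the effect is at most about 0.2-0.9 MFIS points (0.015-0.06 SD) at the assumed slopes and SD. More than that requires systematic imbalance, or a wider age range than the narrow reading of the recruitment focus. The documents do not establish that such imbalance exists; they only fail to rule it out.

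**What to change.** 1. Name the infant's date of birth as a variable recorded at enrolment, and compute weeks since delivery at each visit.
2. Tabulate weeks since delivery by group at baseline and at the 3- and 6-month visits.
3. For fatigue, sleep, mood scores and weight, replace the unadjusted t-tests with a linear model of the follow-up value on group, the baseline value and weeks since delivery at baseline. Pre-specify these covariates so that they do not depend on bivariate significance.

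**Cost.** One date that recruitment already requires, no extra visits or participants, and a regression in place of a t-test, using one or two further degrees of freedom out of 180 planned women. The change does not substitute for stating how women are assigned to the three groups; the plan needs that as well.

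### Objective 2 rests on same-time diet–symptom correlations, which cannot tell a diet effect from symptoms worsening diet; a month-3 to month-6 analysis should be added

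*Combined protocol and SAP*

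**What the plan says.** The document is a single combined protocol and SAP.

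- **Title and objectives.** The title couples adherence with an effect on anxiety, depression, fatigue and sleep quality. Objective 2 is to "Investigate the relationship between MedDiet adherence, obesity, and mental health" over six months.
- **Visits (Study design and setting).** "An intervention study is conducted for lactating mothers with follow-up at 3 and 6 months". No schedule says which questionnaire is given at which visit.
- **Diet measures (A. Questionnaires).** The 14-item MEDAS "is used to assess the adherence of eligible participants to MedDiet"; no reference period is given. The food frequency questionnaire (FFQ) "assesses habitual dietary intake by questioning the frequency with which food items are consumed over one week".
- **Fatigue (A. Questionnaires, MFIS).** "Participants rate the impact of fatigue on their lives over the past 4 weeks".
- **Administration (Instruments).** "All participants are interviewed face-to-face, and trained nutrition researchers fill out questionnaires".
- **Analysis (Statistical analysis).** "Descriptive statistics and correlations for all quantitative and categorical study variables are calculated at baseline and at the end of the study". No lag, change score or adjustment for earlier symptoms is specified. Chi-square tests and regression models are planned for the severity of depression, anxiety and stress. They name neither fatigue nor sleep, do not name adherence as a predictor, and give no time order.

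**The concern.** A correlation between diet and symptoms taken at one time point has no direction. A mother who is tired or low may shop and cook less well, and that gives the same negative correlation as a diet that relieves fatigue. The women enrol when their infants are 1–2 months old, so this reverse path is plausible.

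What is at stake is the reading of objective 2. A significant month-6 correlation, published under a title that speaks of an effect, would probably be taken as support for the diet even if diet did nothing to symptoms. The trial has a visit at 3 months that could place diet before outcome, but the analysis section names only baseline and the end of the study.

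**Working it through.** The plan gives no figure for this analysis, so there is none to reproduce. The check asks how often each analysis would be significant if diet had no effect on fatigue.

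**Inputs.** From the document: 180 women and 20% non-response (Sample size). Treating non-response as loss gives 180 × 0.8 = 144. Assumed: a visit-to-visit correlation of fatigue of 0.5, the path values below, standardised scores, and a two-sided 5% test.

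**Step 1: same-visit correlation.** The chance of significance is approximately Φ(|atanh r| × √(N − 3) − 1.96), with √141 = 11.87.

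*Model A: current fatigue lowers current diet score, so r equals the path.*
- r = -0.1: 0.1003 × 11.87 = 1.19; Φ(-0.77) = 22%
- r = -0.2: 0.2027 × 11.87 = 2.41; Φ(0.45) = 67%
- r = -0.3: 0.3095 × 11.87 = 3.67; Φ(1.71) = 96%

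*Model B: a stable fatigue tendency lowers diet at every visit. Fatigue at a visit is half tendency and half noise in variance, so r = path × √0.5.*
- path -0.2: r = -0.141; Φ(-0.27) = 39%
- path -0.3: r = -0.212; Φ(0.60) = 73%
- path -0.4: r = -0.283; Φ(1.49) = 93%

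**Step 2: adjusted analyses, by simulation** (3,000 to 5,000 trials per setting; ranges are across repeated runs). The baseline-adjusted analysis regresses month-6 fatigue on month-6 diet, baseline fatigue and baseline diet. The lagged analysis regresses month-6 fatigue on month-3 diet, baseline fatigue and month-3 fatigue.

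| Model, path | Same visit | Same visit, baseline-adjusted | Lagged |
|---|---|---|---|
| A, -0.1 | 22% | 20–21% | 5% |
| A, -0.2 | 67% | 64–67% | 5% |
| A, -0.3 | 96% | 94–96% | 5% |
| B, -0.2 | 39% | 15–17% | 10–11% |
| B, -0.3 | 73% | 30% | 18–20% |
| B, -0.4 | 93% | 46–48% | 30% |

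Every entry is a false positive for a diet effect. Baseline adjustment does almost nothing under A and helps only in part under B. The lagged analysis is lowest throughout, but under B it stays above 5%.

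**Step 3: do the recall windows matter?** Let weekly fatigue have autocorrelation ρ, let each week's diet depend on that week's fatigue with path b = -0.4, and let diet have no effect on fatigue (all assumed). Let m be the mean of 1, ρ, ρ², ρ³, and v the variance of the four-week fatigue mean. The correlations are:
- one-week diet with four-week fatigue: b·m/√v
- both over four weeks: b·√v / √(b²v + (1 − b²)/4)
- both over one week: b

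For ρ = 0.6, m = 2.176/4 = 0.544 and v = 9.472/16 = 0.592. The mismatched windows give -0.4 × 0.544/0.769 = -0.28. Both at four weeks gives -0.308/0.552 = -0.56.

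| ρ | Diet 1 wk, fatigue 4 wk | Both 1 wk | Both 4 wk |
|---|---|---|---|
| 0.3 | -0.23 | -0.40 | -0.48 |
| 0.6 | -0.28 | -0.40 | -0.56 |
| 0.9 | -0.37 | -0.40 | -0.63 |

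Unequal windows make the spurious correlation smaller, and equal windows do not remove it. Measuring both at one time is the cause.

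**Step 4: time order under the fix.** With visits at about weeks 13 and 26, the four-week fatigue window at month 6 starts at about week 22, some 9 weeks after the month-3 diet measure.

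**Step 5: group comparison.** When the intervention does not act on fatigue, the simulated between-group difference in fatigue is -0.004 SD, in effect zero.

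**The case against.** **The correlations may be meant as description.** They are listed with the descriptive statistics, objective 2 says relationship, and the effect in the title can be read as that of the education, which is a group comparison. This is fair, and it limits the point to objective 2. But the plan never says that these correlations are non-causal, and it offers no other analysis of adherence against fatigue or sleep.

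**The recall periods.** A reader might infer that the fault lies in asking diet over one week and fatigue over four, so that 21 of 28 days (75%) of the fatigue period come before the diet they are related to. The documents do not support this. The FFQ text does not say past week; it claims habitual intake, and a times-per-week unit fits equally well. MEDAS, the named adherence measure, has no stated period. On the arithmetic above, the mismatch weakens the artefact. For the same reason the FFQ should not simply be relabelled as past-week intake.

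**The lagged analysis is no cure.** This stands. The 5% rate depends on month-3 fatigue blocking the whole reverse path. With a stable tendency behind both measures, 10–30% of trials still mislead.

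**Same-visit administration is inferred.** This also stands: there is no assessment schedule, and collection of these scales at month 3 is not stated. Both sets of measures are nevertheless correlated at the same two time points.

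**Conclusion.** The point holds for objective 2. As written, the plan relates diet to symptoms without time order, and the result cannot distinguish a diet effect from symptoms worsening diet, whatever the recall windows. Under the assumed inputs, with no diet effect, the same-visit correlation is falsely significant in 67–96% of trials when current fatigue drives diet (path -0.2 to -0.3), and in 39–93% when a stable tendency does (path -0.2 to -0.4). The lagged analysis gives about 5% and 10–30% respectively. The paths, the 0.5 correlation and the 144 women are assumptions; at a path of -0.1 under the first model the same-visit rate is 22%.

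A reader might go further and infer that the trial's main comparison is biased. It is not biased by this mechanism, because that comparison is between intervention groups and not between levels of diet. How the groups are formed is not described, but that is a separate matter.

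**What to change.** 1. State that MEDAS, the FFQ and the fatigue, sleep and mood scales are given at month 3 as well as at baseline and month 6.
2. For objective 2, add a time-ordered analysis: month-3 adherence (MEDAS primarily, FFQ second) against month-6 fatigue, sleep and mood, each adjusted for the baseline and month-3 values of the same scale.
3. Label same-visit correlations as descriptive and non-causal.
4. State the reference periods of MEDAS and the FFQ.

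**Cost.** Only plan wording if the scales are already given at month 3; otherwise, extra questionnaires at a visit that is already planned. Only women with both follow-up visits contribute, a short-lived diet effect may look weaker, and confounding by a stable fatigue tendency is reduced but not removed. The report should say so.

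### The plan does not say how women are allocated to the three groups, and its group comparisons adjust for neither site nor baseline score

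*Combined protocol and SAP*

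**What the plan says.** All references are to the combined protocol and SAP.

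- **Design.** Study design and setting reads "An intervention study is conducted for lactating mothers with follow-up at 3 and 6 months", and the sites are "childbirth vaccination clinics in Amman and Irbid, Jordan". The word *randomised* is not applied to this study; it occurs only in the title of a cited reference.
- **Enrolment.** The Sample size section bases its total of 180 on "all eligible candidates who are sequentially enrolled in the study for 6 months".
- **Allocation.** B. Educational Intervention says "The participants are divided into three groups" and then describes education plus brochure, brochure only, and control. It gives no sequence, concealment, stratification or ratio.
- **Aim.** The outcome section states the main aim: "compare the degree of adherence to MedDiet between women who received educational and nutritional interventions during 6 months of follow-up and those without such interventions". Its second part looks for an impact on nutritional status, body measurements and mental health. The title speaks of an effect on anxiety, depression, fatigue and sleep quality.
- **Comparison.** Statistical analysis says "The student's t-test will be used to compare the means and medians of independent variables between groups". A further clause deals with categorical variables: "Pearson's Chi-Square test will be used for categorical data to test for association and probability".
- **Regression.** The same section plans an ordinal logistic regression for determinants of depression, anxiety and stress severity. Its covariates are those with P ≤ 0.05 in bivariate tests.
- **Data collected.** Instruments lists demographic and social factors and mentions possible confounders such as abuse. City, clinic and enrolment date are not in the list.

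**The concern.** A claim that education changed diet or mood needs groups that would have been alike without it. Concealed random allocation provides that by design. Adjustment can provide part of it, for factors that were measured and differ between groups.

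The plan commits to neither. A team could form the groups by city, by clinic, by order of enrolment or by staff choice and still comply with every sentence. Any difference between those sets of women would then enter the group comparison as if it were an effect of the intervention. If two compared arms coincided with the two cities, their data could not separate city from intervention afterwards. The question therefore has to be settled in the plan, not at analysis.

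**Working it through.** **1. Does any part of the plan supply the missing protection?**

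| Possible protection | What the plan contains |
|---|---|
| Random sequence, concealment, stratification, ratio | Not stated |
| City or clinic in the group comparison | Not stated; the t-test and chi-square take no covariates |
| Baseline score in the group comparison | Not stated |
| Multivariable model | One, for depression, anxiety and stress severity; study group, city, clinic, enrolment date and baseline score are not named; covariates are screened by P value; adherence (MEDAS), fatigue and sleep are not covered |
| Use of the collected confounders | None stated for the group comparison |

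**2. How large could the distortion be?** The plan gives no figure for this, so there is none to reproduce. The total of 180 is used only to obtain a group size.

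Inputs:
- Total 180 and 20% non-response, from Sample size.
- Equal arms and equal loss (assumption): 180 / 3 = 60 per arm, and 60 × 0.8 = 48.
- Two-sided 5% level (the plan gives p < 0.05; two-sided is an assumption).
- Cities differ on the outcome by 0.2 or 0.3 SD (assumption; the documents give no value).
- The share of women from one city differs between two arms by 25, 50 or 100 points (assumption).
- No true effect of education.

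Formulas:
- Bias in SD = city difference × difference in city share.
- SE of the difference = √(2/48) = 0.204 SD.
- Noncentrality = bias / SE, with 48 + 48 − 2 = 94 degrees of freedom and critical t about 1.986.
- False-positive rate = P(|t| > critical value) under the noncentral t.

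Example: 0.3 × 1.00 = 0.30 SD; 0.30 / 0.204 = 1.47; rate 0.307.

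| City difference | 25 points | 50 points | 100 points |
|---|---|---|---|
| 0.2 SD | 0.057 | 0.077 | 0.163 |
| 0.3 SD | 0.065 | 0.112 | 0.307 |

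With no loss (60 per arm), the 0.3 SD row becomes 0.069, 0.129 and 0.371.

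For scale, the difference detectable with 80% power at 48 per arm is (1.960 + 0.842) × 0.204 = 0.57 SD. A 0.3 SD bias is about half of that.

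**3. Does adjustment help?** A simulation of 4,000 runs used 60 per arm, a 0.5 SD city difference and city shares of 75% and 25%. The unadjusted test rejected in 25% of runs (27% by the formula, which ignores the extra spread within mixed arms). With city in the model the rate was 5.4%. With equal city shares and city in the model it was 5.1%. Adjustment works here because both arms contain women from both cities. At 100 points, city and group are the same variable within the two arms, and no adjustment of that contrast is possible.

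**The case against.** The strongest reply is that silence is not practice. A reader might infer that women were assigned by city, by date or at staff discretion. The documents do not support that: no sentence links group to any of these, and randomisation left unreported cannot be excluded. The sequential-enrolment wording describes recruitment and is as compatible with randomisation as with anything else. This stands, and it limits the point to what the plan fails to state.

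It can also be said that the plan is not free of adjustment. It collects income, education, smoking and other factors, and it has a multivariable model. That is true and should be acknowledged. The model does not repair the group comparison, for the reasons in the first table of the working, and screening by P value can drop a real confounder. The t-test sentence refers to independent variables, so it is not even certain that it is meant as the outcome analysis. If it is not, no between-group test of a continuous outcome is specified.

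Finally, the 31% and 16% rates need the compared arms to lie wholly in different cities. That is a worst case. With a 25-point difference in city share the excess over 5% is at most 1.5 percentage points at 48 per arm. A reader might take 31% as the expected error rate of this study; nothing in the documents supports that.

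**Conclusion.** The point holds in this form: the allocation method is unstated, and the planned group comparisons take no account of site or baseline score. Following the plan exactly would not justify the words *effect* and *impact* in the title and aim. That makes it more than a missing detail, because the study's main claim rests on it.

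The size is uncertain. Under the stated assumptions, a useless intervention would be declared effective or harmful in about 6% to 31% of studies instead of 5%, depending on how far the cities differ and how unevenly they are spread over the arms. The defect itself follows from the text and does not depend on those figures. It is not established that allocation was haphazard or that any bias has occurred.

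**What to change.** 1. **Women not yet allocated.** State 1:1:1 allocation from a computer-generated, concealed list, stratified at least by city, held by someone who does not recruit and opened only after consent and the baseline interview. Whether clinic can also be a stratum depends on the number of clinics, which the plan does not give.
2. **Analysis.** For every outcome, including MEDAS, DASS-21, MFIS and PSQI, compare the three groups in a model that contains group, the baseline value of that outcome, and city or clinic. Keep the determinants regression as a separate, descriptive analysis.
3. **Women already allocated.** If the method was random, describe it. If it was not, say so. Record city, clinic and enrolment date, and add them to the model with baseline factors listed in advance and not chosen by P value. Word conclusions as association. If any arm lies wholly in one city, state that its contrast with an arm in the other city cannot be separated from the city effect.

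**Cost.** If allocation has not begun, this needs one protocol paragraph, a list and a few model terms. If allocation is complete, step 1 is no longer available and steps 2 and 3 remain; the document does not state how far recruitment has gone. The analysis is slightly more work. Allocating women individually within a clinic may lead them to share the brochure or messages, which would bias the comparison towards no difference; the plan should acknowledge this.
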